5.6.2. Additional considerations

None

5.7. Analysis of safety and reactogenicity

5.7.1. Analysis of safety and reactogenicity planned in the protocol

The primary analysis of safety will be performed on the ES. All analyses will also be performed by age strata (50-69 YOA and ≥ 70 YOA). Following analysis is planned to be performed:

The percentage of subjects with at least 1 local AE (solicited and unsolicited), with at least 1 general AE (solicited and unsolicited) and with any AE (solicited and unsolicited) during the solicited follow-up period will be tabulated with exact 95% CI after each vaccine dose and overall. The percentage of doses followed by at least 1 local AE (solicited and unsolicited), by at least 1 general AE (solicited and unsolicited) and by any AE will be tabulated, with exact 95% CI. The percentage of subjects with at least 1 local AE (solicited only), with at least one general AE (solicited only) and with any AE (solicited only) during the solicited 7-day follow-up period will be tabulated with exact 95% CI after each vaccine dose and overall.

The percentage of subjects reporting each solicited local and general AE during the solicited follow-up period will be tabulated with exact 95% CI. The percentage of doses followed by each individual solicited local and general AE will be tabulated, with exact 95% CI. Fever will be reported *with any ($>=38.0$), $>=38.0 - <=38.5$, $>38.5 - <=39.0$ and >39.0 in GSK scale. In Chinese scale, it will be reported with any ($>=37.3$), $37.3 - <38.0$, $38.0 - <38.5$, $38.5 - <39.5$ and $>=39.5$* . The same tabulation will be performed for fever with causal relationship to the study vaccine.

*In the table presented based on the GSK scale, for all other solicited AEs, the same table will have grade 1, grade 2 and *at least* grade 3 AEs and for any and *at least* grade 3 general AEs with relationship to the study vaccine. Related grade 1 and related grade 2 will also be displayed.*

In the table presented based on the Chinese scale, for all other solicited AEs, the same table will have grade 1, grade 2, grade 3 and grade 4 applicable for table with Chinese intensity scale) AEs and for any, grade 3 and grade 4 general AEs with relationship to the study vaccine. Related grade 1 and related grade 2 will also be displayed.

The proportion of solicited AEs resulting in a medically attended visit will be tabulated.

The percentage of subjects with at least 1 report of unsolicited AE (including cellulitis) classified by MedDRA primary system organ class (SOC) and preferred terms (PT) will be reported within 30 days (Days 1-30) post each vaccination with exact 95% CI. The same tabulation will be performed for grade 3 unsolicited AEs, for unsolicited AEs with a relationship to vaccination, grade 3 unsolicited AEs with a relationship to vaccination.

Number and percentage of any, grade 3, related, grade 3 related and medically attended unsolicited AEs reported within 30 days (Days 1-30) post *any* vaccination according to MedDRA primary system organ class and preferred terms will be presented.

Number and percentage of SAEs from first vaccination up to 12 months post last vaccination will be presented with 95% CI. The same tabulation will also be done for the interval- starting from first vaccination up to 30 days post last vaccination.

Number and percentage of SAEs causally related to vaccination for the interval- starting from first vaccination up to 30 days post last vaccination and from first vaccination up to 12 months post last vaccination and from study start up to study end will be presented with 95% CI.

Number and percentage of subjects experiencing fatal SAEs, classified by MedDRA Primary System Organ Class and Preferred Term will be tabulated using date of onset of SAE for the time periods –from first vaccination up to 30 days post last vaccination and first vaccination up to 12 months post last will be presented with 95% CI.

Number and percentage of fatal SAEs causally related to vaccination for the interval- starting from first vaccination up to 30 days post last vaccination and from first vaccination up to 12 months post last vaccination and from study start up to study end will be presented with 95% CI.

Number and percentage of pIMDs from first vaccination up to 12 months post last vaccination will be presented with 95% CI. The same tabulation will also be done for the interval – starting from first vaccination up to 30 days post last vaccination.

Number and percentage of pIMDs causally related to vaccination from first vaccination up to 12 months post last vaccination will be presented with 95% CI. The same tabulation will also be done for the interval – starting from first vaccination up to 30 days post last vaccination. Number and percentage of serious pIMDs causally related to vaccination from 12 months post last vaccination up to study end and will be presented with 95% CI.

The proportion of subjects with concomitant medication will be tabulated, within 30 days post each vaccination and overall only, with exact 95% CI.

Listing of fatal SAEs, SAEs, pIMDs and withdrawals (from the study or from vaccination) due to AEs, SAEs, solicited and unsolicited AEs will be generated.

Listing of pregnancy during the entire study period will be generated.

Listing for all the suspected HZ episodes will be generated.

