1. SYNOPSIS

Indication:

Shingrix is indicated in China for the prevention of Herpes Zoster (HZ) in adults 50 years of age (YOA) or older.

[figure not shown]
Rationale:

As per requirement of Chinese regulatory authorities, ZOSTER-076 will evaluate the vaccine efficacy (VE), cellular immunogenicity and safety of 2 doses of GlaxoSmithKline Biologicals SA's [GSK's] Recombinant Zoster Vaccine (RZV) vaccine for the prevention of HZ in Chinese adults \geq 50 YOA.

Objectives and Endpoints:

Refer to [Table 7](#).

Overall Design (*Amended, 23 November 2020*):

BS= Blood sampling; N= number of subjects planned to be enrolled; Vacc= Vaccination

Note: [CCI](#)

‡ All subjects will be followed-up until last enrolled subject has completed 1 year of follow-up post last vaccination. In case criteria for vaccine efficacy analyses are not met during this period, the follow-up will be extended.

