10. STATISTICAL CONSIDERATIONS

10.1. Sample size determination

This study is planned to enroll approximately 6138 subjects equally randomized (approximately 3069 subjects) to the RZV and Placebo groups.

The sample size of the study has been determined to have at least 90% power for the confirmatory VE primary objective of $\geq 25\%$ (LL of the 2-sided 95% CI of VE).

Based on the assumption of a true conservative VE of 85% (reference ZOSTER-006 study) for prevention of confirmed HZ cases during the 12 months of follow-up post second dose, a total number of 27 cases of HZ will be needed to demonstrate with at least 90% power that the lower limit (LL) of the 2-sided 95% confidence interval (CI) for the VE is above 25% (By Pass 2012, One Proportion Power Analysis, one-sided test, one-sided alpha=2.5%). In case the number of confirmed HZ cases required for VE evaluation are not met, the follow-up duration will be extended.

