- **End of Study (EoS):** 1) After all the subjects complete their study conclusion contact, occurring within 30 days of the projected study conclusion date of the last enrolled subject, that is, 14 months (approximately 430 days) from the enrolment date of the last subject; In case criteria for VE analyses are not met during this period, the follow-up will be extended and 2) the release of all polymerase chain reaction (PCR) test results for the HZ rash lesion samples. Refer to section 7.1 for more detail.
- **Control:** placebo controlled
- **Vaccination schedule:** 0 and 2 months
- **Treatment allocation:** Eligible subjects will be randomized (1:1) to RZV group or Placebo group. The randomization algorithm will use a stratification procedure accounting for age (50-69 YOA and \geq 70 YOA).
- **Sampling schedule:**
 - CCI [REDACTED]
 - [REDACTED]
 - [REDACTED]
 - Clinical specimens of HZ lesions will be collected from all subjects who are clinically diagnosed with a suspected case of HZ (Section 8.3.2 of the protocol).
 - A urine specimen will be collected from all female subjects of child-bearing potential (see glossary of terms in the protocol definition of woman of child bearing potential) at Visit 1 (Day 1) and Visit 2 (Month 2).
- **Study group and treatment number allocation:** The target will be to enrol approximately 6138 eligible subjects who will be randomly assigned to 2 study groups in a (1:1) ratio (approximately 3069 subjects in each group).

The enrolment will be performed to ensure distribution of the population across the 2 age strata (50-69 YOA and \geq 70 YOA). Approximately 75-80% and 20-25% subject should be enrolled in 50-69 YOA and \geq 70 YOA, respectively. The expected distribution of subjects within these 2 age strata is as shown in [Table 1](#).

To ensure that the collection of date of birth will not jeopardize the privacy of Personally Identifiable Information (PII), only year of birth (YYYY) will be collected.

Table 1 Number of subjects required for enrolment

Age Stratum	Vaccine	Targeted number (%) of subjects
50-69 YOA	RZV	4604-4910 (75-80%)
	Placebo	
\geq 70 YOA	RZV	1228-1534 (20-25%)
	Placebo	

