6. ANALYSIS INTERPRETATION

The primary objective of VE in the prevention of HZ compared to placebo in Chinese adults \geq 50 YOA, as measured by the reduction in HZ risk is considered met if the LL of the 2-sided 95% CI of VE is above 25%.

For all secondary objectives, analyses will be descriptive with the aim to characterize the differences in reactogenicity, safety and immunogenicity between groups.

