10.1.5. Statistical methodology**10.1.5.1. Exact confidence intervals around proportions**

The exact confidence intervals around within-group proportions are derived using the method of Clopper and Pearson [[Clopper](#), 1934].

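### Exact intervals on percent-of-doses rows treat a subject's two doses as independent, so for common events they are too narrow if the two reactions are positively correlated (minor)

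*SAP*

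**What the plan says.** SAP 5.7.1 sets out two families of reactogenicity tables. One counts subjects. The other counts doses, and the dose-level rows are of two kinds:

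- Doses followed by at least one local, general or any AE. The sentence ends: "by at least 1 general AE (solicited and unsolicited) and by any AE will be tabulated, with exact 95% CI".
- Doses followed by each solicited event: "The percentage of doses followed by each individual solicited local and general AE will be tabulated, with exact 95% CI".

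Protocol 10.3.5 has the same two dose-level tabulations, also with exact 95% intervals.

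SAP 10.1.5.1 names one method: "The exact confidence intervals around within-group proportions are derived using the method of Clopper and Pearson". Neither document mentions within-subject correlation, a robust or clustered variance, or resampling by subject for these rows.

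The schedule is two doses at 0 and 2 months. The tables are repeated by age: "All analyses will also be performed by age strata (50-69 YOA and ≥ 70 YOA)". SAP section 6 fixes their status: "For all secondary objectives, analyses will be descriptive with the aim to characterize the differences in reactogenicity, safety and immunogenicity between groups".

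**The concern.** Clopper-Pearson limits come from the binomial distribution, which assumes independent observations with a common probability. A row that pools dose 1 and dose 2 breaks that assumption if a person who reacts to, or reports, the first dose is more likely to do so for the second.

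The documents make such correlation plausible without stating it. The same subject, or a trained assistant, fills in both diary cards (protocol 8.1.1). Many intensity grades depend on what that person tolerates or can still do (protocol Table 26).

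With positive correlation, the number of doses overstates the information in the row. The interval is then narrower than its 95% label justifies. At stake is the stated precision of these rows. No estimate or decision rule depends on it.

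**Working it through.** **The plan's own figure.** The documents give no number for the per-dose intervals. The one sizing figure concerns the primary objective: "a total number of 27 cases of HZ will be needed to demonstrate with at least 90% power". It reproduces:

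- Placebo cases: 2,762 x 0.0085 = 23.5. Total: 23.5 x 1.15 = 27.0. Enrolment: 5,524 / 0.90 = 6,138.
- Conditional on 27 cases, the RZV share is 0.75/1.75 = 0.4286 at VE 25% and 0.15/1.15 = 0.1304 at VE 85%. Rejecting at 6 or fewer RZV cases gives an exact one-sided alpha of 0.0216 and power of 94.7%, which meets the plan's claim.

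This calculation counts HZ cases, not doses, so the point below does not touch it.

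**Inputs for the per-dose rows**

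- Subjects per arm: "randomly assigned to 2 study groups in a (1:1) ratio (approximately 3069 subjects in each group)" (SAP section 3).
- Doses per subject: 2, so up to 3,069 x 2 = 6,138 doses per arm.
- Subjects aged 70 or over: 1,228-1,534 in total (SAP Table 1), so 614-767 per arm. The simulations use 690.
- rho, the correlation between a subject's two binary outcomes: not in the documents, so it is varied.

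**Formula.** With N subjects, two doses each and the same event rate p at both doses:

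Var(p-hat) = p(1-p)(1 + rho) / (2N)

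The binomial method leaves out the factor (1 + rho). The correct width is therefore sqrt(1 + rho) times the stated width, and approximate coverage is 2 Phi(1.96 / sqrt(1 + rho)) - 1. At rho 0.3, sqrt(1.3) = 1.14, 1.96/1.14 = 1.72, and coverage is 91.4%.

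**Coverage for common events.** The simulated column applies Clopper-Pearson to paired data with 3,069 subjects per arm, event rates of 10-70% and 200,000 replicates.

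| rho | Simulated coverage | Formula | Correct width / stated width |
|---|---|---|---|
| 0 | 95.2% | 95.0% | 1.00 |
| 0.1 | 94.1% | 93.8% | 1.05 |
| 0.2 | 92.9% | 92.6% | 1.10 |
| 0.3 | 91.7% | 91.4% | 1.14 |
| 0.5 | 89.4% | 89.0% | 1.22 |
| 0.7 | 87.1% | 86.7% | 1.30 |

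For common events, a correlation of roughly 0.02-0.05 is enough to bring coverage below 95%. A larger sample does not help, because the ratio of widths does not depend on N.

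**Size in percentage points.** At a 50% rate and 6,138 doses, the full Clopper-Pearson width is 2.52 points. The adjusted width is 2.62 (rho 0.1), 2.85 (0.3) or 3.06 (0.5). For those aged 70 or over, at the low end of 614 per arm and rho 0.5, the half-width goes from 1.96 x sqrt(0.25/1,228) = 2.8 to 2.8 x 1.22 = 3.4 points.

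**Departures from the simple model**

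- Unequal rates at the two doses help slightly. With 50% and 30%, coverage at rho 0.3 is 92.4% instead of 91.7%.
- If 10% of subjects had only one dose, the factor would be about 1 + 0.95 rho.
- Rarity helps only when very few events are expected. With 690 subjects aged 70 or over and a 0.1% rate (1,380 x 0.001 = 1.4 expected events), coverage stays above 95% even at rho 0.7. In a full arm at the same rate (6,138 x 0.001 = 6.1 expected events), it is 95.2% at rho 0.1 but 93.2% at 0.3.

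**The case against.** The strongest reply is that little depends on these rows. The secondary analyses are descriptive, and no test or margin uses the intervals. For a full arm the width changes by about half a percentage point at most for rho up to 0.5. SAP 5.7.1 also plans subject-level percentages with exact intervals, which have one observation per subject and are sound. The safety endpoints are framed after each vaccination, so the pooled dose rows are an extra display. All of this stands, and it limits the point to a minor correction.

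A second reply is that rho is unknown. That stands too. Positive correlation is plausible but not documented, and at rho 0.1 the loss of coverage is only about one point.

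A reader might be tempted by three stronger readings:

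- **That every per-dose interval covers less than 95%.** This does not follow. SAP 5.7.1 splits rows by grade, relationship and fever band, and repeats them by age. Some will be very sparse, and there Clopper-Pearson is conservative enough to stay at or above 95%.
- **That the affected intervals will be publicly posted.** The documents do not establish this. SAP 5.7.2 says that the web-disclosure table for solicited events uses both intensity scales. It does not say that the table contains percent-of-doses rows, and table layouts are in a separate document (SAP 10.2).
- **That the efficacy conclusion is affected.** It is not. The vaccine efficacy interval uses first confirmed cases and person-time.

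**Conclusion.** The point holds for percent-of-doses rows with common events, provided that a subject's two outcomes are positively correlated. The stated method then gives intervals that are too narrow: about 94% coverage at rho 0.1, 92% at 0.3 and 89-90% at 0.5, with correct widths about 5%, 14% and 22% larger. The direction is certain under positive correlation. The size rests on an assumed rho and, in the simple formula, on two doses per subject with equal rates.

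This is a minor correction. It is still worth making, because a descriptive interval has no purpose other than to show precision, and the correction is cheap.

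**What to change.** In SAP 10.1.5.1, treat rows whose unit is the dose separately, in one of two ways:

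1. Show the percentage of doses without a confidence interval.
2. Use a subject-clustered interval that tolerates zero counts. One option is Clopper-Pearson on an effective number of doses. Estimate the design effect D as the subject-clustered variance of the percentage divided by p-hat(1 - p-hat)/n, and set D to 1 if it is below 1 or if there are no events. Then compute the limits from x/D events in n/D doses. With no events this reverts to ordinary Clopper-Pearson.

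A plain robust or GEE logit interval, or a clustered ratio interval, is not a safe replacement for all rows, because neither gives a usable interval with zero events. In simulations at a 0.1% rate with 690 subjects, 27-36% of replicates had no events. Counting these as misses, coverage fell to 61-69% for the logit and 64-73% for the ratio, against 97-98% for Clopper-Pearson. In a simulation check the effective-dose version kept coverage at about 95% or more in nearly all settings. It fell slightly short only with about six expected events and strong correlation, where it still did clearly better than the present method.

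Keep Clopper-Pearson for per-subject and single-dose rows. List the change in SAP section 8, since the protocol calls these intervals exact.

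The cost is a short SAP amendment and, for option 2, a change to the per-dose table program. No new data are needed. The downside is slightly wider per-dose intervals, or none under option 1.

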5.7.2. Additional considerations

The table on solicited local and general AEs will be presented separately according to GSK grading and grading scale provided by Chinese authorities.

Duration of each solicited local and general AE during the solicited follow-up period will be presented. Total duration of each individual solicited local and general AE will be tabulated.

Duration of each grade 3 solicited local and general AE during the solicited follow-up period will be presented in the table by GSK grading. Duration of each grade 3 and above solicited local and general AE during the solicited follow-up period will be presented in the table by Chinese authority grading.

Listing of complication related to confirmed HZ episode will be presented.

Number and percentage of subjects experiencing fatal SAEs, classified by MedDRA Primary System Organ Class and Preferred Term will be tabulated using date of onset of SAE from study start up to study end will be presented with 95% CI for web disclosure.

The table for web disclosure related to ***solicited adverse events*** endpoint will be based on both GSK and Chinese intensity scale.

Summary of subjects with serious adverse events related to study participation and not by the study vaccines or to GlaxoSmithKline concomitant medication/vaccine during the entire study period based on ES.

Following listings of concomitant medications related to confirmed HZ episode will be presented based on Exposed Set:

- ***Pain rescue medication to control HZ pain***
- ***Antiviral treatment for HZ***
- ***Other therapy for HZ***

Additional analyses/considerations due to COVID-19 pandemic on ES:

- ***Summary of COVID-19 Assessment.***
- ***Incidence of COVID-19 as an AE and SAE. A standardized MedDRA Query (SMQ) will be used to identify all COVID-19 cases reported as AEs.***
- ***A column to identify COVID-19 AEs/SAEs will be added to listing of (S)AEs and solicited adverse events leading to study or treatment discontinuation from first vaccination up to study end.***

